Safety Assessments:	26. Safety evaluations will include assessment of adverse events (AEs), electrocardiograms (ECGs), cardiac monitoring (telemetry), arterial oxygen saturation (SaO 2 ) using pulse oximetry, vital signs (blood pressure, pulse rate, oral body temperature, and respiration rate), clinical laboratory safety tests (hematology, serum chemistry, liver function tests, thyroid function parameters, serology, coagulation parameters, urinalysis, cytokines, C-reactive protein, complement factors), and physical examinations.
Other Assessments:	

27. Exploratory effects of ALN-TTR02 will be evaluated by:

28. Serial measurement of circulating mutant and wild type TTR levels

	
 
29. Serial measurement of circulating vitamin A and retinol binding protein (RBP) levels
 
Blood collections to explore the expression of hepatocyte derived proteins to further characterize the biological effects of siRNA LNPs.
 

Amendment 2.1 Confidential Page 15 of 116

Dose-Limiting	Dose-limiting toxicities will include any of the following:	
Toxicities and Stopping Criteria:	1. Any life-threatening toxicity.	
Stopping Criteria.	2. ALT and AST ≥5 × ULN or total bilirubin >2.0 mg/dL.	
	3. An infusion reaction that requires hospitalization, despite premedication.	
	4. Any other toxicity which in the opinion of the SRC precludes further dosing.	
	Stopping Rules:	
	For any DLT, accrual to that dose level will stop, all dosing will be discontinued, and dose escalation will end, pending further evaluation of all available safety data by the SRC.	
Statistical Methods:	Statistical analyses will be primarily descriptive in nature.  Adverse event summaries will include tabulations of all treatment-emergent AEs, treatment-related AEs, serious adverse events (SAEs), discontinuations due to AEs, and AEs of various grading severity. By-patient listings will be provided for deaths, SAEs, and AEs leading to discontinuation of treatment.	
	Descriptive statistics will be provided for clinical laboratory data, vital signs data, and ECG interval data, presented as both actual values and changes from baseline relative to each onstudy evaluation. Laboratory shift tables from baseline to worst values will be presented.	

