### 7.2.7.1 Hematology, Serum Chemistries, and Urinalysis

Blood samples for hematology and serum chemistries and urine for urinalysis are to be collected at Screening, pre-dose on Day 0 (unless the screening evaluations were performed within the previous 72 hours) and Day 28 (or Day 21 for optional cohorts dosed once every 3 weeks), and on the Day 1, 14, 29, 42, and 56 study visits (or Days 1, 14, 22, 35, and 56 for optional cohorts dosed once every 3 weeks), or at the time of early termination, if applicable.

Prior to discharge from the hospital on Days 1 and 29 (or Days 1 and 22 for optional cohorts dosed once every 3 weeks), local serum laboratories (specifically, sodium, potassium, creatinine, albumin, calcium, glucose, and phosphate) must be reviewed by the Investigator and the results deemed not clinically significant. Any clinically significant findings must be discussed with the medical monitor to determine whether patient can be discharged and to formulate plans for patient follow-up.

Blood for CRP is to be collected pre-dose (within 10 minutes) on Days 0 and 28 (or Days 0 and 21 for optional cohorts dosed once every 3 weeks), and at 2 and 6 hours ( $\pm 15$  minutes), and 24 hours ( $\pm 120$  minutes) post-infusion.

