### 7.2.7.5 Thyroid Function Tests

Blood for thyroid function tests is to be collected at Screening, pre-dose on Days 0 (unless the screening evaluations were performed within the previous 72 hours) and 28 (or Days 0 and 21 for optional cohorts dosed once every 3 weeks), and at Day 14, 42, and 56 (or Days 14, 35, and 56 for optional cohorts dosed once every 3 weeks) study visits, or

at the time of early termination, if applicable. These samples are to be processed at the site's local laboratory.

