# 9.2 Statistical Methodology

Statistical analyses will be primarily descriptive in nature. Adverse event summaries will include tabulations of all treatment-emergent AEs, treatment-related AEs, SAEs, discontinuations due to AEs, and AEs of various grading severity. By-patient listings will be provided for deaths, SAEs, and AEs leading to discontinuation of treatment.

Descriptive statistics will be provided for clinical laboratory data, vital signs data, and ECG interval data, presented as both actual values and changes from baseline relative to each on-study evaluation. Laboratory shift tables from baseline to worst values will be presented.

Tabulations will be presented by dose level. For categorical variables, summary tabulations of the number and percentage of patients within each category (with a category for missing data) will be presented. For continuous variables, the number of patients, mean, median, standard deviation, minimum, and maximum values will be presented.

All data will be provided in by-patient listings.

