4.5.3. Laboratory Data

Clinical laboratory values will be expressed in SI units.

Descriptive statistics will be provided for the actual values and changes from baseline to each on-study evaluation for each clinical laboratory parameter, including hematology, clinical chemistry, LFTs, thyroid function tests, and coagulation studies. Percent change from baseline will also be summarized.

Descriptive statistics will be provided for CRP and cytokines at pre-dose and 2, 6, and 24 hours post-dose. Change from pre-dose will also be summarized. Fold change, as defined below, will be summarized for CRP. Complement factor (Bb) will be summarized at pre-dose, and 30 minutes, 2 hours and 24 hours post-dose. Change and fold change from pre-dose will also be summarized. Separate summaries will be presented for Dose 1 and Dose 2.

Fold change from pre-dose is defined as the ratio of the post-dose value to the pre-dose value. Maximum fold change is defined as the ratio of the maximum post-dose value to the pre-dose value. Maximum fold change from pre-dose for cytokines, complement factor (Bb), and CRP will be represented graphically in the form of a semi- \log_{10} plot. Maximum fold change will be plotted for each subject, grouped by dose level. Data recorded as below the limit of detection will be set equal the lower limit of detection for the calculation of fold change. Separate plots will be presented for Dose 1 and Dose 2.

For each continuous laboratory parameter, results will be categorized as low, normal, or high based on the laboratory normal ranges. Shift tables will be employed to summarize the pre-dose category versus the post-dose category, where the post-dose category will be based on the maximum observed value (in absolute value) subsequent to each dose. For dose 1, the maximum value shall be selected from assessments performed through the Day 28 pre-dose

value (Day 21 for the 3-week regimen). All out-of-range and clinically significant laboratory results will be identified in subject data listings.

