5. CHANGES TO PLANNED ANALYSES

As of this date, there have been no changes between the protocol-defined statistical analyses and those presented in this SAP.

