Table 14.3.5.8	Shifts from Pre-Dose in Laboratory Parameters, by Dose Group (Intent-to-Treat Analysis Set)
Table 14.3.5.9	Summary and Change from Pre-Dose for Serial Vital Signs and SaO ₂ by Time Point, by Dose Group (Intent-to-Treat Analysis Set)
Table 14.3.5.10	Summary and Change from Pre-Dose for Electrocardiogram Results by Visit (Intent-to-Treat Analysis Set)

Table 14.4.1	Study Drug Exposure (Intent-to-Treat Analysis Set)
Table 14.4.2	Concomitant Medications, Overall and by Dose Group (Intent-to-Treat Analysis Set)
Table 14.4.3	Premedications, Overall and by Dose Group (Intent-to-Treat Analysis Set)

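### The laboratory shift table classes each continuous parameter by its post-dose maximum, so it misses any fall not present at every assessment in the dose period; the protocol promises worst values.

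*SAP*

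**What the plan says.** Protocol synopsis (Statistical Methods): "Laboratory shift tables from baseline to worst values will be presented". Protocol 9.2 repeats the commitment: "Laboratory shift tables from baseline to worst values".

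SAP 4.5.3 grades each continuous laboratory parameter as low, normal or high against the laboratory's range and cross-tabulates the pre-dose category with a post-dose category, "where the post-dose category will be based on the maximum observed value (in absolute value) subsequent to each dose". It then fixes the window: "For dose 1, the maximum value shall be selected from assessments performed through the Day 28 pre-dose" value (Day 21 for the 3-week regimen). No parameter is excepted, and no minimum-based or direction-specific shift is planned.

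The output is Table 14.3.5.8, "Shifts from Pre-Dose in Laboratory Parameters, by Dose Group", the only laboratory shift table in SAP 7.1. SAP Section 5 says that "there have been no changes between the protocol-defined statistical analyses and those presented in this SAP".

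**The concern.** For ALT, AST or bilirubin the worst value is the highest, and the SAP rule finds it. For haemoglobin, neutrophils, platelets and albumin the direction of concern is downward: the eligibility criteria in Protocol 4.2 set lower limits for all four. For those parameters the maximum is the best value in the period. For electrolytes, glucose, calcium and thyroid tests either direction can matter, and the rule covers only one. T4 is relevant here because Protocol 1.1.1 says TTR carries about 15% of it in plasma, and SAP 1.2.5.2 lists change in thyroid function among the safety evaluations.

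A patient whose value falls below range and recovers would therefore appear as normal, or as high. Safety is the primary objective, and this is the only planned table that counts patients moving across normal limits. A reader who takes it as a worst-value table, as the protocol describes it, would see too few falls.

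**Working it through.** The documents give no figure to reproduce here. The check is one of logic, then counting, then an illustration under stated assumptions.

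**1. What the rule selects.** The parameters are counts, concentrations, times or ratios, none negative, so |x| = x and the maximum in absolute value is the ordinary maximum. For fixed normal limits, the category of the maximum is the highest category observed. The result is low only if every assessment in the period is low. For example, take neutrophils of 6.0, 0.8 and 3.5 with a normal range of 2.0 to 7.5 (all assumed): the maximum, 6.0, gives normal; the minimum, 0.8, gives low.

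**2. Assessments per dose period (4-week regimen).**
- Haematology and chemistry are drawn before dosing and "on the Day 1, 14, 29, 42, and 56 study visits" (Protocol 7.2.7.1): k = 3 after dose 1 (Days 1, 14, 28 pre-dose) and k = 3 after dose 2 (Days 29, 42, 56).
- Thyroid tests are drawn before dosing "and at Day 14, 42, and 56" (Protocol 7.2.7.5): k = 2 after dose 1 (Days 14, 28 pre-dose) and k = 2 after dose 2 (Days 42, 56).
- Coagulation (Protocol 7.2.7.4): k = 2 after dose 1 (Days 1, 28 pre-dose) and k = 1 after dose 2 (Day 29).

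**3. Pattern counts, with no probability assumption.** With each value low or not low, 2^k − 1 patterns contain at least one low value, and only one (all low) is classed low.
- k = 3: 2^3 − 1 = 7 patterns, 6 missed.
- k = 2: 2^2 − 1 = 3 patterns, 2 missed.
- k = 1: 1 pattern, none missed.

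With three categories, the number of sequences containing a low value is 3^k − 2^k: 27 − 8 = 19 for k = 3 (18 missed) and 9 − 4 = 5 for k = 2 (4 missed). These are counts of possible sequences, not frequencies. Under a minimum-based rule for the low direction, none is missed.

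**4. Share of patients with any low value who are still classed low.** Let p be the probability of a low value at one visit. The share is P(all k low) / P(at least one low). For independent visits this is p^k / (1 − (1 − p)^k); for example, with p = 0.3 and k = 3, 0.027 / 0.657 = 0.041. Correlated visits use an equicorrelated Gaussian latent variable with correlation ρ, integrated numerically. Both p and ρ are assumptions.

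| k | ρ | p = 0.1 | p = 0.3 | p = 0.5 |
|---|---|---|---|---|
| 3 | 0 | 0.004 | 0.041 | 0.143 |
| 3 | 0.5 | 0.071 | 0.190 | 0.333 |
| 3 | 0.8 | 0.237 | 0.393 | 0.530 |
| 3 | 0.95 | 0.508 | 0.641 | 0.737 |
| 2 | 0 | 0.053 | 0.176 | 0.333 |
| 2 | 0.5 | 0.193 | 0.354 | 0.500 |
| 2 | 0.8 | 0.391 | 0.543 | 0.660 |
| 2 | 0.95 | 0.638 | 0.744 | 0.816 |

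**5. In patients.** Taking p = 0.3 and ρ = 0.8 over the maximum of 27 patients:
- k = 3: 11.8 expected to have a low value, 4.6 classed low, 11.8 − 4.6 = 7.2 missed.
- k = 2: 10.5 with a low value, 5.7 classed low, 10.5 − 5.7 = 4.8 missed.

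**The case against.** **Drafting slip.** The absolute-value phrase makes sense only if the largest deviation or change was meant, and both the protocol wording and SAP Section 5 suggest a two-sided rule was intended. That is plausible. But the SAP mentions neither deviation nor change, and its next sentence again calls for the maximum. A programmer following the text would code the maximum, so the text needs correcting whatever was intended.

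**Low values are visible elsewhere.** This is true. By-visit summaries print the minimum (SAP 3.2), out-of-range values are listed separately (Table 14.3.4), and laboratory findings can be recorded as adverse events (Protocol 8.1 and 8.3) and so counted in the adverse event tables. None of these counts patients moving from normal to low. Routine tests are run at each centre's local laboratory (Protocol 7.2.7), at up to 10 centres, so a pooled minimum need not show whether a value was below the range that applied to it.

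**No decision depends on the table.** Also true. The numeric laboratory limits in the dose-limiting toxicity definition are upward (ALT, AST, bilirubin), the Safety Review Committee sees data during the study, and no formal testing is planned. This limits the consequence without removing the contradiction.

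**The magnitudes are assumed.** They are, and their range is wide. The 27-patient example also pools patients whom the table splits by dose group. In addition, no passage calls a low T4 harmful. The conclusion rests on the logic of step 1 and needs none of these figures.

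**Conclusion.** The concern holds. As written, SAP 4.5.3 replaces the protocol's worst value with the maximum for each continuous laboratory parameter, and SAP Section 5 does not declare it. Any fall that is not present at every assessment in the dose period is lost from Table 14.3.5.8.

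The scope is narrow. It covers continuous parameters only (urinalysis is listed, not summarised) and only dose periods with more than one assessment, so coagulation after dose 2 is unaffected. Sustained falls and all rises are classed correctly. The logic assumes that a patient's normal limits do not change within the period. The number of patients affected cannot be derived from the documents; even with visits correlated at 0.95, the assumed range leaves 18% to 49% of patients with a low value not shown as low. It is a correction to one descriptive safety table and should be made before programming.

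**What to change.** In SAP 4.5.3, replace the single rule with two shifts for each dose period: pre-dose category to the category of the post-dose minimum (for low), and pre-dose category to the category of the post-dose maximum (for high). Alternatively, define the worst direction for each parameter and use that extreme. Delete the absolute-value phrase and align the sentence on the dose 1 window. If the maximum-only rule is deliberate, record it in SAP Section 5 as a departure from the protocol and say so in the table title.

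The cost is one revised sentence, a consequential edit to the next, and one more set of columns in Table 14.3.5.8. No new data are needed.

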4.5.4. Vital Signs and Physical Examination

Descriptive statistics will be provided for serial vital signs collected on each dosing day, including blood pressure, pulse rate, oral body temperature and respiration rate. Pulse oximetry (SaO₂) will be included with serial vital sign summaries. Change from pre-dose to each post-dose assessment will also be summarized. Treatment group means with standard error bars will be plotted over time for each serial vital sign assessment. Separate plots will be presented for Dose 1 and Dose 2. Routine vital signs will be included in subject listings but will not be summarized.

Vital sign measurements will be presented for each subject in a data listing. All physical examination findings will be presented in a data listing.

4.5.5. Electrocardiogram

Descriptive statistics will be provided for serial ECGs collected on each dosing day, including ventricular rate, PR interval, QRS duration, and QT interval. Bazett's formula will be used to calculate the heart rate corrected QT interval (QTcB). The mean of the triplicate values will be used for calculating summary statistics. Change from pre-dose to each post-dose assessment

will also be summarized. Routine 12-lead ECGs will be included in subject listings but will not be summarized.

Electrocardiogram data for each subject will be provided in a data listing.

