If infusion reaction: Tryptase and C3a u				X	X								
Premedication v		X	X										
Premedication reminder w		X											
Study Drug Administration				$X^{x}$									
Anti-PEG Antibody Testing (IgG, IgM)	X		X				X				X		X
Cytokines and CRP y			X	X	X								
Plasma PK Sampling z			X	X	X	X	X		X	X	X	X	X
Urine PK Sampling aa			X	X	X	X	X		X	X	X	X	X
Exploratory Biomarkers	X		$X^{bb}$		X	X	X	X	X	X	X		
Concomitant Medications	X						Continuo	us Monito	ring				
Review/Record AEs									_				
Study Completion											X		

Footnotes on following pages.

Note: The schedule of assessments for optional cohorts administered ALN-TTR02 once every 3 weeks is provided in Appendix 4.

- a Early termination procedures: if a patient withdraws prior to Day 56, then the Days 56 and 208 visits should be performed. If a patient is withdrawn/withdraws after Day 56 and prior to Day 208, then the Day 208 visit should be performed.
- b Interval medical history.
- c Focused physical examination (includes head/ears/eyes/nose/throat [HEENT], cardiovascular, respiratory, abdominal, and hepatic assessments). If the screening physical examination was performed within 72 hours of Day 0, then the pre-dose (Day 0) physical examination does not need to be repeated; however, the patient's weight will be obtained.
- d Weight measured on Day 0 and Day 28 will be used for calculating first and second dose, respectively.
- e Vital signs to include: blood pressure, pulse rate, oral body temperature, and respiratory rate. Parameters are to be measured in the supine position using an automated instrument after the patient has rested comfortably for 10 minutes.
- f Serial measures (vital signs and pulse oximetry) are to be measured within 30 minutes pre-dose; at the end of infusion (EOI); and 30 (±5) minutes; 1, 2, and 3 (±15 minutes) hours; 6, 12, and 18 (±30 minutes) hours; and 24 (+30 minutes) hours post-infusion.
- g Not needed if a normal echocardiogram has been obtained within the past 90 days.
- h Serial electrocardiograms (ECGs) will be collected in 3 replicates within 30 minutes pre-dose, EOI, and 30 (±5) minutes, 2 and 4 (±15 minutes) hours, and 24 (+30 minutes) hours post-infusion.

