### 7.2.4 Electrocardiogram

Computerised 12-lead ECG recordings will be obtained. Each lead shall be recorded for at least 3 beats at a speed of 25 mm/s. Triplicate recordings will be made at the time points indicated in Table 1-1.

Serial ECGs will be collected in triplicate 30 minutes prior to dosing (Days 0 and 28 [or Days 0 and 21 for optional cohorts dosed once every 3 weeks]), EOI, and 30 (±5) minutes, 2 and 4 (±15 minutes) hours, and on Days 1 and 29 (or Days 1 and 22 for optional cohorts dosed once every 3 weeks) at 24 (+30 minutes) hours post-infusion.

The following electrophysiologic parameters will be assessed: rhythm, ventricular rate, PR interval, QRS duration, and QT interval. Either Bazett's and/or Fridericia's formula will be used to calculate the heart rate corrected QT interval (QTc).

The Investigator or designee is responsible for reviewing the ECG to assess whether the ECG is within normal limits and to determine the clinical significance of the results. Prior to discharge from the hospital on Days 1 and 29 (or Days 1 and 22 for optional cohorts dosed once every 3 weeks), the ECG must be reviewed by the Investigator and the results deemed not clinically significant. Any clinically significant findings must be discussed with the medical monitor to determine whether patient can be discharged and to formulate plans for patient follow-up.

For any clinically significant abnormal results, the Investigator must contact the Medical Monitor to discuss continued participation of the patient in the study (e.g., ischemic ECG changes, wave/interval changes, or arrhythmia).

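### The SAP summarises QTc by Bazett's formula alone; adding Fridericia beside it would help separate a heart-rate shift around the infusion from a change in QTc

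*SAP*

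**What the plan says.** Protocol 7.2.4 leaves the choice open: "Either Bazett's and/or Fridericia's formula will be used to calculate the heart rate corrected QT interval (QTc"). SAP 4.5.5 settles it: Bazett's "formula will be used to calculate the heart rate corrected QT interval (QTcB"). QTcF is mentioned neither there nor in the table list, where ECG results are in Table 14.3.5.10. SAP section 5 declares no change from the protocol analyses.

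The same SAP section also summarises the other serial ECG variables, "including ventricular rate, PR interval, QRS duration, and QT interval", with change from pre-dose to each post-dose assessment. On replicates it says: "The mean of the triplicate values will be used for calculating summary statistics". On individual data: "Electrocardiogram data for each subject will be provided in a data listing".

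On timing, footnote h of the protocol's Table 1-1 says that serial ECGs "will be collected in 3 replicates within 30 minutes pre-dose, EOI, and 30 (±5) minutes, 2 and 4 (±15 minutes) hours", with a further set at 24 hours. SAP 1.2.5.2 names serial ECGs as one measure of infusion tolerability, and safety is the primary objective.

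**The concern.** Bazett divides QT by the square root of RR. If QT in these patients shortens less steeply than that as the heart speeds up, the formula over-corrects when rate rises and under-corrects when it falls. A change in rate then enters the QTc column as if it were a change in repolarisation: upwards with a faster rate, and downwards, possibly hiding a real prolongation, with a slower one.

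The setting makes this worth checking. Most of the serial ECGs fall between the end of infusion and 4 hours after it, when an infusion reaction, its treatment or the premedication may change heart rate. Protocol 5.5 has two premedication regimens, one oral and one largely intravenous, so rate could also differ between groups. The study has a single arm, so no concurrent control shows what the same rate change does to QTcB without study drug. Cohorts have three patients, so one patient can move a group mean. At stake is how a descriptive table under the primary safety objective is read.

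**Working it through.** Neither document gives a QTc value, an expected heart-rate change or a QTc threshold, so there is no planned figure to reproduce. What follows is an illustration.

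**Inputs.** From the documents: the two named formulas, the ECG times and cohorts of three. Assumed, because the documents are silent: no drug effect on repolarisation; QT = Q × RR^b with RR = 60/rate in seconds; Q = 400 ms (range 380 to 440); resting rate 70 bpm (range 60 to 80); b from 0.25 to 0.5.

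**Formulas.**

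- QTcB = QT / RR^(1/2) = Q × RR^(b - 1/2)
- QTcF = QT / RR^(1/3) = Q × RR^(b - 1/3)

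QTcB is therefore independent of rate only at b = 1/2, and QTcF only at b = 1/3. For any b below 1/2 the exponent on RR in QTcB is negative, so a faster rate raises it.

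**Step 1: b = 1/3.** Here QTcB = 400 × (rate/60)^(1/6), and QTcF stays at 400 ms by construction.

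| Rate (bpm) | QTcB (ms) | Change from 70 bpm (ms) |
|---|---|---|
| 70 | 410.4 | 0 |
| 75 | 415.2 | +4.7 (from unrounded values) |
| 80 | 419.6 | +9.2 |
| 90 | 428.0 | +17.6 |

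A fall from 80 to 70 bpm gives 410.4 - 419.6 = -9.2 ms.

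**Step 2: other starting values, still b = 1/3.** A 10 bpm rise gives +10.4 ms from a resting rate of 60 and +8.3 ms from 80 (Q = 400). From 70 bpm it gives +8.8 ms at Q = 380 and +10.2 ms at Q = 440.

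**Step 3: the exponent.** For 70 to 80 bpm, Q = 400:

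| b | QTcB change (ms) | QTcF change (ms) | Difference (ms) |
|---|---|---|---|
| 0.25 | +14.1 | +4.5 | 9.6 |
| 1/3 | +9.2 | 0 | 9.2 |
| 0.4 | +5.5 | -3.5 | 9.0 |
| 0.5 | 0 | -8.6 | 8.6 |

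The gap between the two formulas is about 9 ms in every row. What depends on b is which formula carries the error. Between 1/3 and 1/2 the two changes bracket the true value of zero.

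**Step 4: effect on a small group.** One patient of three with the 20 bpm rise of Step 1 moves the group mean QTcB by 17.6/3 = 5.9 ms.

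**The case against.** A reader might infer that the SAP has broken a protocol commitment to Fridericia. It has not. The protocol's wording lets the sponsor use Bazett alone, and the SAP's statement of no changes is consistent with that.

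A reader might also infer that Fridericia is the right correction and should replace Bazett. Step 1 cannot show this, because holding QTcF constant assumes it. Step 3 shows that Fridericia has its own error whenever b is not 1/3, and nothing in the documents fixes b for these patients. This supports reporting both.

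The best defence is what the plan already provides. Ventricular rate and uncorrected QT are summarised with change from pre-dose. SAP 4.5.4 does the same for serial pulse rate and plots it for each dose. Every patient's ECG data are listed. A reader could see that a QTcB shift follows rate. The pre-dose ECG, within 30 minutes of dosing, will usually come after premedication, so part of any premedication effect is already in the reference value. The analysis is descriptive: there is no test, no QTc category, and QTc is not among the dose-limiting toxicities in Protocol 5.7.3. Safety during the trial relies on investigator review of tracings and on telemetry.

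Most of this stands, and it limits the consequence. It does not supply the missing number. The rate and QT summaries let a reader suspect a rate effect, but mean QTcF cannot be recovered exactly from group means of QT and rate. Someone would have to recompute it from the listings.

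**Conclusion.** The point holds as a modest one. Using Bazett alone is allowed, but it leaves the reported QTc change open to distortion by heart rate in either direction if b is below 0.5. Under the stated assumptions the distortion is about 5 ms for 5 bpm, 9 ms for 10 bpm and 18 ms for 20 bpm. The heart rates, the 400 ms and the exponent are all assumptions.

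It would go too far to infer that any heart-rate rise will appear as QTc prolongation. The size depends on the rate change and on b, it is zero at b = 0.5, and the documents do not say that rate will change at all. Severity is minor to moderate: no formal decision depends on QTcB, and the data needed to recognise a rate effect are already collected. This is a free improvement to a safety summary, not the repair of an error.

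**What to change.** In SAP 4.5.5, derive QTcF from the QT and ventricular rate already collected, handling triplicates in the same way as for QTcB. In Table 14.3.5.10, show QTcF and its change from pre-dose beside QTcB at each time point, separately for each dose. Add one sentence on reading the table: a QTcB shift that QTcF does not show is to be interpreted together with the change in ventricular rate.

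The cost is one derived variable and some extra rows in an existing table. No new data are needed, and no protocol amendment, because Protocol 7.2.4 already permits both formulas.
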